<sup>b 1, 2, 3 or 4 as per Maya-Enero et al.

<sup>c Visibly jaundiced (parent/carer noted), visibly jaundiced (HCP noted), risk factors, routine, unwell, incidental

<sup>dRole of staff member performing measurement, Value and units, Location on body, Brand and model of machine, Time of measurement, Date of measurement eRole of staff member performing measurement, Value and units, Value relative to treatment line (micromol/L above/below line), Type of SBR (blood gas, lab, spun bili),

Time of measurement, Date of measurement

fNo intervention, feeding plan implemented (e.g. not specified, breastfeeding support, top ups), repeat bilirubin assessment indicated at a later time point (with time point specified), commence single phototherapy, commence double phototherapy, admit to NICU

Received IVIG, received exchange transfusion

hWhich of the following investigations were performed and what were their results: DAT, G6PD, blood cultures, participant blood group, birthing parent's blood group.

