#### **Primary Objective 1**

We will be using a linear mixed effects model, where the confounders will be adjusted for as fixed effects, and hospitals will be fitted as a random effect. Due to the complexity of the model we will be using, the optimal method of calculating the sample size requirement *a priori* is with simulation, using *simr* in R^12. We use the following simulated dataset:

[figure not shown]
- Exposure Our exposure, skin tone, will be on 4 levels, with 1 being the lightest and 4 the darkest. No recent research on skin tone within London has been found, therefore we refer to the latest UK census results for ethnicity. For a conservative estimate, we will simulate the data for ethnicity that we would expect in London to act as a proxy for skin tone, as with the 6 categories of ethnicity (White (53.8%), Black (13.5%), Asian (20.7%), Mixed (5.7%) and Other (6.3%)). Therefore we simulate data with probability 50%, 20%, 20% and 10% for tones 1,2,3 and 4, respectively.
- We assume that we will have 20 hospitals collecting data, therefore we have 20 clusters to be a random effect
- The outcome will be simulated depending on skin tone and age. Age will be uniformly distributed between ages 0 and 96 hours. Bilirubin mean will be simulated according to the following formula:
  - Bilirubin (μmol/L)=2.6\*age (hours)+60+20\*skin tone+60 with standard deviation 10. The coefficient and intercept, 2.6 and 60 respectively, is to fit the line where babies begin to need phototherapy according to the NICE jaundice treatment threshold graphs.

We wish to achieve an effect size of 10 µmol/L for skintone 2 compared to skin tone 1, 20 µmol/L for skin tone 3 compared to skin tone 1, and 30 µmol/L for skintone 4

compared to 1. We perform 100 simulations for each simulated cluster size (between cluster sizes of 10 and 50 neonates), and estimate the average power achieved. Assuming a 95% confidence interval (CI), we can plot the number in each cluster against the estimated power.

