## **Primary Objective 2**

We approximate a sample size needed for Bland-Altman plots. We calculate the minimum sample size needed to detect a difference. A prior study found the following measurements:

	Mean [SD] (mcmol/L)
Colour 1	106 [43]
Colour 2	108 [38]
Colour 3	113 [38]
Colour 4	145 [34]

From this, we take a mean difference of 10 to be our estimated effect size. From above, we take the two largest standard deviations for a cautious estimate of the standard dedication of difference (SD= $\sqrt{43^2+38^2}=57.4$ ). We set our targeted clinical agreement limit at 145 mcmol/L. Under these assumptions, a sample size of 80% requires 140 study participants , which from above we should easily exceed.

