Primary objective 1 will be using a linear mixed model, with skin tone and confounders as fixed effects and hospital as a random effect. The outcomes will be the coefficient difference between baseline skin tone and the other 3, with 95% CI.

Primary objective 2 will use the Bland-Altman to detect differences of measurement between skin tones, stratified by method of how the measurement for how serum bilirubin was taken. The mean of the differences will be provided with 95% CI, along with the IQR of difference with accompanying p-value. The rate of over/under-estimation will also be estimated between different skin tones. Bland-Altman plots will be reported as well as Specificity and sensitivity analyses using Receiver operating characteristic (ROC) curves.

Secondary Objective 1: Primary length of admission differences between skin tone will be compared using survival analysis of time to event data (Kaplan-Meier plot, Cox Proportional Hazards Model). The need for interventions including phototherapy and exchange transfusion will be done using generalised linear mixed models, with outcomes reported as Odds Ratios with 95% CI.

Age of infant at measurement is an important metric and shall be included as a fixed covariate in all models other than Bland-Altman (baseline model). Additionally, IMD and gestational age may be included as additional covariates (adjusted model). However, due to the complex relationship between skin colour and medical intervention, we run the risk of over-adjusting on covariates and inducing collider bias and/or mediators. For example, skin tone may affect what the indication for jaundice assessment was, and this in turn may affect the outcome of bilirubin and if there was a delay for treatment, making it a mediator. With sufficient time, this relationship may be explored to see if different skin tones are affected by how their jaundice is first indicated, which influences clinical guidelines if an association is found between skin tone and indication which in turn affects bilirubin levels.

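### The TcB–SBR agreement analysis for Primary Objective 2 neither limits nor adjusts for the time between the two readings, although both times are collected

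*Protocol*

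**What the plan says.** Section 10.2 (Method of analysis) fixes the method: "Primary objective 2 will use the Bland-Altman to detect differences of measurement between skin tones, stratified by method" of obtaining the serum value. SBR method is the only stratifier. The outputs are the mean difference with its confidence interval, the IQR of the differences, over- and under-estimation rates, Bland-Altman plots and ROC curves.

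On timing, the same section says that infant age at measurement "shall be included as a fixed covariate in all models other than Bland-Altman (baseline model". This is the infant's postnatal age, not the time between TcB and SBR.

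The interval can be derived from planned data. The Table 1 footnotes in Section 8 list for TcB "Brand and model of machine, Time of measurement, Date of measurement" and for SBR "Type of SBR (blood gas, lab, spun bili" followed by "Time of measurement, Date of measurement".

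The study does not control the interval. Section 9 (Laboratory assessments) leaves SBR to the clinical team, and Section 7 describes SBR as following a TcB that lies close enough to the treatment line. The only window tied to a bilirubin measurement is in Section 8: twelve hours, for the skin-tone inspection.

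For the repeated sample-size re-estimation, Section 10.2 allows bilirubin values, skin tone and age at TcB, and nothing else. SBR time is not on that list.

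**The concern.** A difference between two readings taken at different times has two parts: device disagreement, and change in the infant's bilirubin between the readings. A raw difference cannot separate them. Bilirubin may rise while the SBR is awaited, or fall if treatment starts first, so the sign of the error is not fixed.

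Two results are at stake. The overall mean TcB–SBR difference is shifted by the average change over the interval. The comparison between tones, which is what the objective is about, is shifted if the average interval differs by tone. The protocol itself makes that plausible:

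- Section 10.2 accepts that skin tone may affect the indication for assessment and delay in treatment.
- Section 8 allows recruitment to reopen at centres where a given tone group is more likely to be found, which links tone to hospital.
- Section 8 (guideline and local practice information) plans to extract the local TcB thresholds for SBR and departures from national guidance, so practice may differ by site.
- The Bland-Altman analysis, unlike the Objective 1 model, has no hospital term.

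A site difference in the time from TcB to SBR could then be read as a tone difference in TcB accuracy. The over- and under-estimation rates and ROC curves would use the same pairs.

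**Working it through.** **Inputs.**
- Slope 2.6 µmol/L per hour (Section 10.1, Objective 1: "The coefficient and intercept, 2.6 and 60 respectively"). It was chosen to follow the phototherapy treatment line and is not an observed rate of rise within an infant.
- Mean difference 10 µmol/L (Section 10.1, Objective 2: "we take a mean difference of 10 to be our estimated effect size").
- SD of differences 57.4, agreement limit 145, N = 140 for 80% power (same place). Alpha is not stated there; two-sided 0.05 is assumed.
- Distribution of the interval: not given, so gaps below are illustrative.

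**The plan's own figures.** √(43² + 38²) = √3293 = 57.38, which matches 57.4. With the SE of a limit taken as SD × √(1/n + 1.96²/(2(n − 1))) and non-central t, the printed inputs give N = 152, and power 0.77 at N = 140. An SD truncated to 57 gives N = 141. The mismatch with 140 is a separate matter.

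**Shift in the mean difference.** Shift in SBR − TcB = slope × gap, with SBR taken second.

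| Gap (h) | Shift at 2.6 µmol/L per hour |
|---|---|
| 0.5 | 1.3 |
| 1 | 2.6 |
| 2 | 5.2 |
| 4 | 10.4 |
| 6 | 15.6 |

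Gap that equals the assumed mean difference: 10 / 2.6 = 3.85 h. For assumed slopes of 3.5 and 1 it is 10 / 3.5 = 2.9 h and 10 / 1 = 10 h.

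**Shift in the comparison between tones.** With a common slope, shift = slope × (mean gap in one tone − mean gap in the reference tone). Equal mean gaps give zero, whatever their length. A 1 h difference in mean gap gives 2.6 and a 2 h difference gives 5.2.

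**Widening of the limits.** Half-width = 1.96 × √(SD² + (slope × SD of gap)²), with the gap independent of device error.
- SD 57.4, gap SD 4 h: 1.96 × √(57.4² + 10.4²) = 114.3, against 1.96 × 57.4 = 112.5.
- Assumed SD 20, gap SD 4 h: 44.2 against 39.2.

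**Effect on the Objective 2 power calculation.** If the rise adds to the assumed 10, a uniform 2 h gap makes the mean 15.2; power at N = 140 falls from 0.77 to 0.54 and N needed is 254. A 4 h gap makes it 20.4, with power 0.31 and N = 516. If the existing difference has the opposite sign, the rise would partly cancel it, so these figures show sensitivity only.

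**The case against.** The strongest reply is that choosing the pairs, setting a maximum interval and handling treatment between readings are analysis-set definitions usually left to a SAP, and Section 10.2 mentions SAP text that is not at hand. Nothing in the protocol forbids a window, both times are collected, and Table 1 places both readings at enrolment, which suggests one assessment episode. This stands in part. Against it, the synopsis in Section 4 sends the reader to Section 10 for the detailed plan, and Section 10 chooses a stratifier without mentioning the interval. The closed list of data for re-estimation is also protocol text, which a SAP rule alone would not change.

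A reader might infer more than the documents support:

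- *That the age sentence removes time from the agreement analysis.* It concerns postnatal age. A standard Bland-Altman analysis has no covariates, and adjusting for age would not remove an interval effect.
- *That pairs are admitted at any interval by rule.* The protocol is silent; it states no such rule.
- *That gaps of up to twelve hours are foreseen.* That figure belongs to the skin-tone inspection.
- *That a 3.8 h difference in delay would reproduce a between-tone effect of 10.* Section 10.1 uses the 10 as the mean difference in a Bland-Altman calculation and does not establish it as a between-tone difference in accuracy. Nothing in the documents shows delays that far apart.
- *That the limits of agreement would be materially widened.* At the protocol's SD they would not.

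**Conclusion.** The point holds as a gap in a primary analysis. As Section 10.2 stands, change in true bilirubin between the two readings is counted as device disagreement, and the recorded times are not used to prevent it. The overall mean difference is biased whenever the average change is not zero. The comparison between tones is biased only if the delay, or the rate of change, differs by tone, directly or through hospital; a delay common to all tones leaves it intact.

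The size is indicative: about 2.6 µmol/L per hour of gap, so roughly 3.8 h matches the assumed 10, with a range of 2.9 to 10 h for assumed slopes of 3.5 to 1. This rests on a treatment-line slope standing in for an infant's rate of rise, on SBR following TcB, and on no treatment in between. The actual bias cannot be computed without the interval distribution. The limits move by under 2% at SD 57.4 (112.5 to 114.3, even at a gap SD of 4 h); they would move visibly only if the true SD is much smaller.

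**What to change.** In Section 10.2, adopt one of the following for Primary Objective 2, or state where the rule is set:

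1. Regress the TcB–SBR difference on skin tone with the signed TcB-to-SBR interval as covariate, keeping the SBR-method strata. Report the mean difference at zero interval, and limits from the residual SD. This keeps all pairs, but assumes a roughly linear change over the interval, so pairs with treatment between readings must be flagged or set aside.
2. Restrict the primary agreement set to pairs within a prespecified short interval and before treatment, with other windows as sensitivity analyses. The documents give no basis for a particular length; it should be fixed before differences are examined by tone.

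With either option, tabulate the interval by skin tone and by hospital, and use the same pairs for the over- and under-estimation rates and ROC curves. Add SBR time to the data that Section 10.2 allows for re-estimation, so that the Objective 2 inputs are updated on the same basis.

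Cost: a wording change, with no new data for the interval itself. A window loses some pairs; the covariate approach by itself loses none. A rule on treated pairs may need one more item: Table 1 records a plan to start phototherapy but lists no start time.

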### Secondary Objective 2:

Data collected for Secondary Objective 2 consists of web-based survey responses regarding local practice from local leads at each site, as well as any available guidelines and relevant information leaflets. Information extracted from these guidelines will focus on mentions of skin tone, use of routine jaundice screening, thresholds to perform SBRs based on TcB readings, deviation from national guidelines, and availability of community jaundice assessments and/or treatment. A narrative synthesis will be conducted.

# Secondary Objective 3:

Free text answers from the parent survey and transcripts from focus groups and semi-structured interviews will be analysed using a thematic content approach consisting of six steps: familiarisation, coding, generating themes, reviewing themes, defining and naming themes, and writing up. This method will reduce confirmation bias when reviewing data. An inductive approach will be employed during familiarisation, to allow the data to determine themes and a latent approach will be used when analysing the data in order for the coding to consider the subtext and assumptions that may underlie the explicit content of the data. Qualitative manuscripts will utilise the Consolidated criteria for reporting qualitative research (COREQ) checklist.

#### 11. Ethics

We will seek ethical approval from the NHS / HSC Research Ethics Committees via the IRAS system. The project IRAS application is currently in progress (identifying number 339043). Local approvals will be sought from each participating hospital site. These applications will be led by the local leads for each trust. Data collection will be started in sites where the project is approved even if we are waiting on approvals for other sites.

Anticipated risks are low but may centre around acceptability of the skin tone tool use and language around race or ethnicity.

Considering results from our pre-study patient and public involvement (PPI) survey, we have clarified the language used to explain the study and skin tone assessment process. As successfully done for this initial survey, we plan to translate all study materials into languages most relevant to the study population (as per the Office for National Statistics data). We further aim to minimise risks of parental distress around these topics including sensitive training for data collectors and maintaining a parent representative as a key part of the team throughout the study. Parents will be offered the opportunity to feedback anonymously when enrolling into the study, allowing them to raise any negative experiences with research staff. Feedback will be monitored and acted on in real time.

Risks of data breach will be minimised by the use of a pseudonymised, encrypted data collection tools including (REDCap) within our data Safehaven and the NHS Microsoft 365 Forms platform.

There is a risk that the consenting process could delay initiation of treatment for a jaundiced baby. It will be clearly stipulated within research team training, that any urgent clinical management is prioritised and carried out simultaneously. Given the unblinded nature of the study, healthcare professional perception of need for tests could be affected. Study training will emphasise that the overall number of tests carried out should not increase due to a site's participation in this study. All those working on the study will be GCP trained to minimise risks of harm.

## 12. Public involvement

As this project focuses on identifying how current neonatal practices contribute to health inequalities, we recognize that families' insights and experiences will be key in understanding current challenges and in planning how to deliver better health outcomes in the future.

We have prioritised patient and public engagement from the project conception, which has allowed study co-production with parent and carer perspectives and priorities at the forefront. As the project is centred around newborn babies, we gathered views from new parents and carers through a web-based scoping survey that included:

- Their understanding of jaundice in the neonatal period, and any previous experience of this
- The impact of their ethnicity on jaundice assessments by healthcare professionals
- How to best explain our project to future participants

 How they would feel about the use of a skin tone tool on their baby, and the language we use around this

The survey was available in 10 languages, to maximise accessibility and reach a diverse audience. Survey links were disseminated via posters and parent whatsapp groups, both through community parent groups and the resident doctor-led REACH network. The network includes local leads at a number of London sites which allowed us to gather insights from parents across Barts Health as well as other London trusts. Please see Appendix 1 for a summary of survey findings.

There are currently three parent representatives within the study team, who are reviewing the initial versions of the study protocol and participant information sheet. They will continue to play a key role in our team throughout the study. A PPI focus group has been held with 5 parents, centred around the Participant Information Sheet and a roleplay of a study team member approaching a parent regarding the study. Feedback was positive and no parent would have opted out of the study. Please see Appendix 2 for a summary of the focus group feedback.

The parent / carer survey, focus groups and semi-structured interviews will be collecting qualitative data on what may be challenging topics and as such, our parent representatives play an important role in ensuring the content of these is as accessible, clear and sensitive as possible. Parents enrolled in the study who would like to feedback or contribute ideas to the study methodology, will have the ability to do so via the feedback link in the participant information sheet.

Parental engagement is crucial in the ongoing study co-production, analysis and dissemination of findings. Representatives will continue to be invited to regular research team meetings and to review amended project protocols to ensure we continue to meet the needs of our study participants. They will be involved in discussions around the analysis of our results in particular when analysing qualitative datasets and considering key themes that have been extracted. Parents will be particularly crucial in guiding the effective publication and dissemination of study findings across both academic and public forums, with the aim to effect improvements in the way we assess jaundice in babies of all backgrounds and skin tones.

# 13. Data handling and record keeping

#### 13.1. Data management

Study methodology is described in more detail in section 9. On study recruitment days, local leads will inform all postnatal ward staff responsible for jaundice detection to flag potentially eligible patients. During the data collection period, all neonates undergoing their first jaundice investigations will be approached for recruitment. Enrollment processes will not delay routine clinical care. Data on the value of the first bilirubin reading including the diagnostic method(s) used, alongside a number of covariates, will be collected.

Site teams will impute study data into a standardised data collection form using REDCap electronic data capture tools hosted at QMUL on a secure server and accessed via a password protected link on NHS Trust password-secured computers.

Only pseudonymised data will be entered. Age will be entered in hours of life using an online calculator at the point of data entry with no date of birth data being recorded. Deprivation status will be used by entering the postcode locally into a deprivation code calculator and on the collection form only the deprivation code but not the postcode will be entered. Data completeness and validity will be enhanced by making essential data mandatory for submission to REDCap, data validation rules being inbuilt in the database as well as regular incompleteness and discrepancies with any such issues to be resolved through discussion with local teams and on consensus discussion between REACH project leads. Study recruitment logs will be completed contemporaneously with most clinical data collected at recruitment; final diagnosis, management required and relevant test results may be added subsequently.

Qualitative data on carer experience of newborn jaundice will be collected through the parent / carer survey on the NHS Trust Microsoft 365 Forms web-based application. This will be accessed via a link or QR code on the participant information leaflet. No patient identifiable data will be collected here and data will be encrypted. Parent in-person focus groups and semi-structured interviews will be audio-recorded and transcribed for data extraction and thematic analysis. Recordings will not include patient identifiable data and will be stored securely within Microsoft Sharepoint. These sessions will not include specific parent details e.g. name, date of birth, or address. However, data generated may include thematic analysis and quotes which could possibly be identifiable by either study participants themselves or those close to them. While we do not anticipate that this would be identifiable to others, we will warn participants that direct quotes may be used, to ensure transparency.

